10.5 Dose Modifications for Toxicity

The investigator (in consultation with the Sponsor's medical monitor as needed) will decide whether any AE that occurs is related to either or both drugs and determine whether dose modification or discontinuation of one or both drugs is required per the guidance below.

10.5.1 FLX475

For ongoing DLT assessment throughout both parts of the study, subjects will be monitored closely for treatment-emergent AEs (TEAEs) and laboratory abnormalities. [REDACTED]

[REDACTED]

[REDACTED]

If a subject experiences an AE, appropriate supportive care (e.g., antiemetics, antidiarrheals) should be instituted according to the nature of the event. In general, dose modifications of FLX475 are not permitted during the DLT Observation Period (Days 1–21 of Cycle 1). Subjects who experience a DLT during Cycle 1 should discontinue study treatment (unless it is determined to be in the subject's best interest to continue treatment by the investigator in consultation with the Sponsor's medical monitor).

For subjects receiving study treatment beyond Cycle 1, the following dose modification and discontinuation guidelines for FLX475 below should be considered. (Note that AEs known to be associated with ipilimumab but not previously observed with FLX475 monotherapy may not require modification of FLX475 dose.)

- For any clinically-significant organ-related Grade 4 TEAE (neurologic, pulmonary, cardiac, gastrointestinal, genitourinary, renal, hepatic, cutaneous) at least possibly related to FLX475, discontinue drug use permanently (unless it is determined by the investigator, in consultation with the Sponsor's medical monitor, to be in the subject's best interest to continue treatment, at a reduced dose).
- For subjects with average Grade 2 or 3 QTcF prolongation at doses of 75 mg or greater (measured at times other than during the up to 6-hour period immediately following an FLX475 dose when a threshold of Grade 3 QTcF prolongation should be used), interrupt treatment with FLX475 until resolution to Grade 0 or 1 or to the pretreatment severity grade, then resume treatment at 50 mg. Subjects with average Grade 2 or 3 QTcF prolongation while at the 50 mg or lower dose level of FLX475 (measured at times other than during the up to 6-hour period immediately following an FLX475 dose when a threshold of Grade 3 QTcF prolongation should be used) should be permanently discontinued from FLX475 treatment (unless it is determined by the investigator, in consultation with the Sponsor's medical monitor, to be in the subject's best interest to continue treatment either at 50 mg or at a reduced dose of 25 mg). Any subjects with observed QTcF prolongation of potential significance should have the ECG repeated for confirmation and electrolytes assessed and replaced as needed prior to action with study drug being taken. Any subjects with observed Grade 4 QTcF prolongation (including symptomatic/serious arrhythmia) should be treated appropriately and permanently discontinued from FLX475 treatment (unless it is later determined by the investigator, in consultation with the Sponsor's medical monitor, to be in the subject's best interest to continue treatment).
- The investigator may interrupt treatment with FLX475 for any other AE considered unacceptable for the individual subject, and treatment may be resumed at the previous lower dose level when resolved to Grade 0 or 1 or to pretreatment severity grade.
- If no lower dose level exists to which the subject may de-escalate, FLX475 should be discontinued.

Other dose modifications may be acceptable but should be implemented at the investigator's discretion in consultation with the Sponsor's medical monitor, considering the subject's condition and the clinical benefit to the subject of continuing treatment at the current dose. If the subject requires a dose modification for an AE, then FLX475 administration should be interrupted, as necessary (and upon consultation with the Sponsor's medical monitor), until the AE resolves or stabilizes to an acceptable degree (generally to CTCAE Grade 0 or 1 or to pretreatment severity grade). Thereafter, treatment with FLX475 may be reinstated at the previous lower dose level. Subsequent reductions to successively lower dose levels can be made, if needed, as shown in [Table 2](#). More frequent laboratory monitoring may be required. Once the dose of study treatment has been reduced, it may not be increased at a later date without approval from the Sponsor's medical monitor. (Note that AEs known to be associated with ipilimumab may not require interruption or modification of FLX475 dosing.)

Table 2 Dose Modification Guidelines for FLX475-Related Toxicity

Treatment-Related Toxicity ^{a,b}	Management	Dose Adjustment
Grade 1 or Tolerable Grade 2		
	Continue treatment	No change
Intolerable Grade 2^c or Grade 3^{d, e}		
First occurrence	Interrupt FLX475 until resolved to Grade 0–1 or tolerable Grade 2 (or baseline)	Reduce FLX475 dose by 1 level (or if no lower dose level exists, discontinue drug)
Second occurrence (same toxicity or new toxicity)	Interrupt FLX475	Discuss with Sponsor
Grade 4^f: Discontinue Study Treatment		

Note: For grading see CTCAE version 5.0 ([Appendix 1](#)). Collect all CTC grades of adverse events, decreasing and increasing grade.

BMI = body mass index, CTCAE = Common Terminology Criteria for Adverse Events.

- a An interruption of study treatment for more than 21 days will require Sponsor's approval before treatment can be resumed.
- b Initiate optimal medical management for nausea, vomiting, hypothyroidism and/or diarrhea prior to any study treatment interruption or dose reduction.
- c Applicable only to Grade 2 toxicities judged by the subject or physician to be intolerable.
- d For Grade 3 toxicity, investigator will decide the probability of the event being related to 1 or both drugs and as to whether dose modification of either or both drugs is required.
- e For asymptomatic laboratory abnormalities, such as Grade ≥ 3 elevations of amylase and lipase that are not considered clinically relevant by the investigator, continuation of treatment should be discussed with the Sponsor.
- f Excluding laboratory abnormalities judged to be non-life-threatening, in which case manage as Grade 3.

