6.1.3.2 Clinical Experience with FLX475

6.1.3.2.1 FLX475-01: Phase 1 Healthy Volunteer Study

FLX475 has been studied in a Phase 1, first-in-human, randomized, double-blind, placebo-controlled trial in the Netherlands examining the safety, pharmacokinetics (PK), and pharmacodynamics (PD) of both single and repeat dosing of FLX475 in healthy volunteers (van Marle et al., 2018). Seven cohorts of 8 subjects each (6 drug, 2 placebo) were administered single doses ranging from 5 mg to 1000 mg. Six cohorts were administered daily doses of FLX475 for 14 days ranging from 25 mg to 150 mg, including two cohorts evaluating a 300 mg loading dose administered on Day 1.

FLX475 was well-tolerated, with no significant laboratory abnormalities or dose-limiting clinical adverse events. Dose-dependent increases in exposure were observed with low peak-to-trough ratios and a half-life of approximately 72 hours. Daily dosing without a loading dose demonstrated approximately 4–5x accumulation of FLX475 over 14 days. The tablet formulation of FLX475 to be used in the oncology study was shown to provide equivalent exposure as the capsule formulation used in the healthy volunteer (HV) study, suggesting the HV PK data are applicable to the planned study in cancer patients. In addition, there was no significant effect of food on the bioavailability or PK profile of FLX475 tablets. A receptor occupancy (RO) PD assay using study subject peripheral blood T_{reg} demonstrated a tight PK/PD relationship, suggesting that doses of approximately 75 mg PO QD and above are sufficient to maintain target drug exposure above the IC₉₀ for human in vitro T_{reg} migration.

The most common adverse events reported were transient low-grade headache and gastrointestinal symptoms (e.g. loose stool, abdominal discomfort, vomiting) that were considered not, unlikely, or possibly related to study medication. Asymptomatic transient Grade 1 and 2 prolongations in QTc interval were occasionally observed during dose escalation. An increased number of QTc interval increases were observed at the highest dose cohorts which achieved mean C_{max} values approximately 3–5-fold greater than the target therapeutic exposure level. There was no notable increase in QTc interval prolongation events observed at dose levels and exposures within the target exposure range for clinical efficacy.

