6.2 Risk-Benefit Assessment

FLX475, also known as F003475, is an orally-available, potent, and selective small molecule antagonist of CCR4. In preclinical models of cancer, it has been shown to inhibit the recruitment of T_{reg} into tumors, and to improve tumor control and eradication in combination with CPIs. Refer to the FLX475 Investigator's Brochure for details.

Based on the non-clinical toxicology studies performed, a starting dose of

In the clinical

experience in healthy volunteers and in subjects with advanced cancer to date ([Section 6.1.3.2.2](#)), only asymptomatic and reversible QTcF prolongation has been observed as a dose-related effect of FLX475, and a daily oral dose of 100 mg FLX475 has been chosen as the recommended Phase 2 dose of FLX475 to be used in subjects with advanced cancer, both as monotherapy, and in combination with pembrolizumab.

Thus, based on the available preclinical, non-clinical, and clinical data, the risk-benefit profile of FLX475 is judged acceptable for this proposed Phase 2 study in subjects with advanced melanoma. No significant safety findings have been observed [[Section 6.1.3.2](#)] that would alter the risk-benefit profile of this proposed phase 2 study testing FLX475 combination therapy with ipilimumab in subjects with advanced or metastatic melanoma. Because the proposed mechanism of action of FLX475 is the specific CCR4-mediated inhibition of recruitment of T_{reg} into tumors, and not a global inhibition or depletion of T_{reg} activity, it is not expected that FLX475 will result in significant autoimmunity or generalized immune activation. Consistent with this hypothesis, no clinical or histopathologic signs of cytokine release, autoimmunity, or inflammation were observed in non-clinical studies or in healthy volunteers or cancer subjects to date.

The safety profile of ipilimumab has been well described, and does include immune-mediated toxicity ([Yervoy® Package Insert](#)). Based on its proposed mechanism of action, FLX475 is not expected to significantly enhance immune-mediated toxicity when administered with ipilimumab. Consistent with this, no overlapping toxicity with pembrolizumab has been observed to date. However, signs and symptoms of immune-mediated toxicity (e.g., autoimmunity) will be closely monitored in the clinic and appropriate supportive care measures will be administered as indicated.

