10 TREATMENTS

10.1 Overview of Treatments Administered

Subjects will take FLX475 orally once daily (QD) starting on Day 1 of Cycle 1. See [Section 10.2.1](#) for details of the planned dose administration schema.

Subjects will also receive ipilimumab. Ipilimumab 3 mg/kg will be administered IV Q3W for up to four doses.

The treatments to be used in this study are outlined in [Table 1](#).

Table 1 Study Treatments

Study Treatment	Formulation	Dose Levels	Route of Administration	Sourcing
FLX475	Tablets	100 mg (with possible dose reduction to 75, 50, or 25 mg) qd	Oral	Provided centrally by the Sponsor
Ipilimumab	Solution for infusion	3 mg/kg Q3W	IV infusion	Provided by the site

IV = intravenous, Q3W = once every 3 weeks, qd = once daily.

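### Beyond Cycle 1, the QTcF text in Protocol Section 10.5.1 and Table 2 give different default FLX475 dose actions for the same Grade 2–3 QTcF prolongation

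*Protocol*

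**What the plan says.** Protocol Section 10.5.1 first sets the period. For Days 1–21 it says that, in general, "dose modifications of FLX475 are not permitted during the DLT Observation Period (Days 1–21 of Cycle 1"). The guidance that follows is introduced with "For subjects receiving study treatment beyond Cycle 1, the following dose modification and discontinuation guidelines for FLX475 below should be considered".

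One bullet then deals with QTcF alone:

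- At 75 mg or more, average Grade 2 or 3 prolongation means "interrupt treatment with FLX475 until resolution to Grade 0 or 1 or to the pretreatment severity grade, then resume treatment at 50 mg".
- At 50 mg or lower, the default is to stop FLX475 for good. The subject may continue at 50 or 25 mg if that is judged to be in the subject's best interest.
- At Grade 4, FLX475 is stopped for good, again with a best-interest exception.
- In the period of up to 6 hours after a dose, the threshold for action is Grade 3.

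Table 2, later in the same section, is titled as guidance for FLX475-related toxicity:

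- The row "Grade 1 or Tolerable Grade 2" keeps treatment and dose as they are.
- For a first intolerable Grade 2 or Grade 3, FLX475 is interrupted until Grade 0–1, a tolerable Grade 2 or baseline. The adjustment is then "Reduce FLX475 dose by 1 level (or if no lower dose level exists, discontinue drug").
- At Grade 4, study treatment is discontinued. A footnote excepts non-life-threatening laboratory abnormalities.

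The footnotes mention nausea, vomiting, hypothyroidism, diarrhea, amylase and lipase. None mentions QTcF.

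The dose ladder is in Table 1 (Section 10.1): "100 mg (with possible dose reduction to 75, 50, or 25 mg) qd". Section 6.2 states that "only asymptomatic and reversible QTcF prolongation has been observed as a dose-related effect of FLX475".

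**The concern.** The bullet and the table sit in one section, cover the same period and can both be applied to the same ECG. An asymptomatic Grade 2 prolongation that neither subject nor physician finds intolerable falls naturally into the table's no-change row, yet the bullet calls for a hold and a lower dose. A site working from the table and a site working from the text could therefore act differently, on the one effect the protocol describes as dose-related.

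Three things depend on this:

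- **Safety management.** The same finding may or may not lead to an interruption.
- **Exposure.** Section 6.1.3.2.1 suggests that "doses of approximately 75 mg PO QD and above are sufficient to maintain target drug exposure". After a first Grade 3 on 100 mg, the table leaves the subject at 75 mg. The text leaves the subject at 50 mg, which is 1 − 50/75 = one third lower.
- **Deviation coding.** SAP Section 7.3.2 treats an incorrect dose as an important or major deviation, and Protocol Section 12.1.1 requires no major deviation for a subject to count as evaluable. Resuming at 75 mg follows Table 2 and departs from the bullet.

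**Working it through.** The plan gives no figure to reproduce. The check applies each rule to every first-occurrence case and compares the default dose action.

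**Inputs.** Dose levels 100, 75, 50 and 25 mg come from Table 1. Gradings are tolerable Grade 2, intolerable Grade 2 and Grade 3, as in Table 2. The ECG is beyond Cycle 1 and outside the 6-hour post-dose period, and the event is attributed to FLX475.

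**Rules.**

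- Text: any of the three gradings gives 50 mg if the dose is 75 mg or more, and a permanent stop (default) if it is 50 mg or less.
- Table 2: tolerable Grade 2 leaves the dose unchanged. Intolerable Grade 2 or Grade 3 moves one level down, or stops if there is no lower level.

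| Dose | Grading | Text default | Table 2 | Same dose? |
|---|---|---|---|---|
| 100 mg | Tolerable Grade 2 | 50 mg | 100 mg | No |
| 100 mg | Intolerable Grade 2 | 50 mg | 75 mg | No |
| 100 mg | Grade 3 | 50 mg | 75 mg | No |
| 75 mg | Tolerable Grade 2 | 50 mg | 75 mg | No |
| 75 mg | Intolerable Grade 2 | 50 mg | 50 mg | Yes |
| 75 mg | Grade 3 | 50 mg | 50 mg | Yes |
| 50 mg | Tolerable Grade 2 | Stop | 50 mg | No |
| 50 mg | Intolerable Grade 2 | Stop | 25 mg | No |
| 50 mg | Grade 3 | Stop | 25 mg | No |
| 25 mg | Tolerable Grade 2 | Stop | 25 mg | No |
| 25 mg | Intolerable Grade 2 | Stop | Stop | Yes |
| 25 mg | Grade 3 | Stop | Stop | Yes |

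**Count.** Differences by dose level are 3 + 1 + 3 + 1 = 8 of 12. All three gradings differ at 100 mg, the study dose.

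**Sensitivity to the best-interest exception.** The text lets a subject on 50 mg or less continue at 50 or 25 mg by exception. Suppose that exception were always used, and always landed on the table's dose. The 3 + 1 = 4 differences at 50 and 25 mg would then go, leaving 8 − 4 = 4 of 12, all at 75 or 100 mg, where the text gives no such exception.

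**Resume threshold.** The text requires Grade 0–1 or the pretreatment grade. The table also accepts a tolerable Grade 2. So even where the dose agrees (intolerable Grade 2 or Grade 3 at 75 mg), the time of restart can differ.

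**Grade 4.** The text stops FLX475 and allows an exception. The table discontinues study treatment and gives no exception that names QTcF.

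**The case against.** The best answer is that a specific rule overrides a general one. The QTcF bullet is detailed, and the bullet after it is addressed to adverse events other than those already covered. The paragraph before Table 2 opens by speaking of further dose modifications. All of this is guidance to be considered, with the medical monitor available for consultation. A careful reader may well take the bullet to govern QTcF.

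That reading is reasonable, but it remains an inference. Table 2's title takes in all FLX475-related toxicity, and its footnotes make exceptions for other findings but not for QTcF. Consultation does not tell a site which default it starts from.

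Three stronger readings are tempting, and the documents do not support them.

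- **That the Cycle 1 rule is a third conflicting action for the same ECG.** The scope sentence limits the bullets to treatment beyond Cycle 1, so the Cycle 1 rule covers a different period. At most an edge case is left: the ±3-day visit window allows the Day 22 visit to fall as early as Study Day 19 (22 − 3), inside the DLT period.
- **That a non-DLT prolongation in Cycle 1 gets no action.** The restriction holds only in general, Section 10.5 leaves dose decisions to the investigator, and part of Section 10.5.1 is blacked out. Nor can the gap be shown by pairing baselines of 441–449 msec with QTcF values of 501–509 msec. The rise exceeds 60 msec in 36 of the 81 whole-msec pairs (509 − 441 = 68, for example), which meets the DLT criterion. The 450 msec eligibility limit also applies to the screening ECG, whereas the DLT baseline is the C1D1 pre-dose average.
- **That the earlier study shows how often this would arise.** In FLX475-02 monotherapy, QTc DLTs occurred in (1 + 1)/(7 + 6) = 2 of 13 subjects at 75 and 100 mg. Both had confounding factors, and no DLTs were seen in evaluable subjects given pembrolizumab as well. These are DLTs, not the Grade 2–3 events at issue here, so no rate follows.

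**Conclusion.** The point stands as an inconsistency between text and table beyond Cycle 1. Default dose actions differ in 8 of 12 first-occurrence cases, including every grading at 100 mg. The resume threshold and the Grade 4 action differ as well. The conflict is not universal: the two agree on dose for intolerable Grade 2 and Grade 3 at 75 mg and at 25 mg.

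This rests on grades as the protocol names them (it does not print the msec cut-offs), on Table 1 as the ladder for one level down, and on defaults rather than exceptions. Nothing is inferred from the blacked-out text.

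The consequences should not be overstated. The documents do not show that sites acted differently, and they do not give the number of subjects affected. The healthy-volunteer statement makes about 75 mg sufficient for target exposure; it does not say that a lower dose is inactive. SAP Sections 7.4.1 and 7.7 report early discontinuation and drop the efficacy summaries, so no effect on a reported response rate can be claimed. What remains is the handling of the drug's only reported dose-related effect, and how FLX475 dosing is judged when deviations are classified.

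**What to change.** Reconcile the QTcF bullet in Section 10.5.1 with Table 2 and its footnotes, so that each combination of QTcF grade and dose level has one default action and one resume threshold, Grade 4 included. State in Table 2 which rule covers QTcF. Which dose, threshold or rule applies is for the sponsor to decide.

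The cost is a row or footnote in Table 2 and matching wording in the bullet, issued through the change procedure in Section 14.1. No new assessments are needed. Because the study ended early, the clinical study report should also say which rule was used when FLX475 dosing after a QTcF event was classified as compliant or as a deviation.

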10.5.2 Dose Modification for Ipilimumab

Adverse events associated with ipilimumab exposure may represent an immunologic etiology and may affect more than one body system simultaneously. These immune-related AEs (irAEs) may occur shortly after the first dose or several months after the final dose of ipilimumab. Therefore, early recognition and initiation of treatment is critical to reduce complications. Based on existing clinical study data, most irAEs are reversible and can be managed with interruptions of ipilimumab, administration of corticosteroids, and/or other supportive care. Suspected irAEs should be adequately evaluated to confirm etiology or exclude other causes. Additional procedures or tests such as bronchoscopy, endoscopy, skin biopsy may be included as part of the evaluation. Based on the severity of irAEs, ipilimumab should be withheld or permanently discontinued, and corticosteroids administered. Ipilimumab may cause severe or life-threatening infusion-reactions including severe hypersensitivity or anaphylaxis. Signs and symptoms usually develop during or shortly after drug infusion and generally resolve completely within 24 hours of completion of infusion. Note that modification of dosing of ipilimumab (e.g. withholding or discontinuation) due to

potential/likely ipilimumab toxicity (e.g. irAE) does not require similar modification of FLX475 dosing unless there is evidence of concurrent FLX475-related toxicity.

Thorough dose modification and toxicity management guidelines for irAEs associated with immunotherapies including ipilimumab have been published and should be followed ([Brahmer, et al., 2018](#)). Criteria for dose delay, modification, or discontinuation of ipilimumab are described below. Additional guidance regarding dose modification for ipilimumab can be found in Section 2.3 of the approved label ([Yervoy® Package Insert](#)).

[Table 3](#) shows treatment guidelines, including premedications, for subjects who experience an infusion reaction associated with the administration of ipilimumab. Examples of some of the most common irAEs are provided in [Table 4](#).

Ipilimumab may be interrupted for situations other than treatment-related AEs, such as medical/surgical events or logistical reasons not related to study treatment. Ipilimumab should be restarted within 3 weeks of the scheduled interruption, unless otherwise discussed with the Sponsor. The timing of restarting ipilimumab should be discussed with and agreed to by the Sponsor's medical monitor. The reason for interruption should be documented in the subject's eCRF.

Table 3 Infusion Reaction Treatment Guidelines for Ipilimumab

NCI CTCAE Grade	Treatment	Premedication for Subsequent Doses of Ipilimumab
Grade 1 Mild reaction; infusion interruption not indicated; intervention not indicated	Increase monitoring of vital signs as medically indicated until the subject is deemed medically stable in the opinion of the investigator.	None
Grade 2 Requires infusion interruption but responds promptly to symptomatic treatment (e.g., antihistamines, NSAIDs, narcotics, IV fluids); prophylactic medications indicated for ≤ 24 h	
Stop infusion and monitor symptoms. Additional appropriate medical therapy may include but is not limited to:
 
IV fluids Antihistamines NSAIDs Acetaminophen Narcotics
 
Increase monitoring of vital signs as medically indicated until the subject is deemed medically stable in the opinion of the investigator.
 
If symptoms resolve within 1 hour of stopping drug infusion, the infusion may be restarted at 50% of the original infusion rate. Otherwise ipilimumab administration will be held until symptoms resolve and the subject should be premedicated for the next scheduled dose.
 
Subjects who develop Grade 2 toxicity despite adequate premedication should permanently discontinue study treatment.
	Subject may be premedicated 1.5 h (± 30 minutes) prior to infusion of ipilimumab with: Diphenhydramine 50 mg orally (or equivalent dose of antihistamine). Acetaminophen 500–1000 mg orally (or equivalent dose of antipyretic).

NCI CTCAE Grade	Treatment	Premedication for Subsequent Doses of Ipilimumab
